9.4.4 SAFETY ANALYSES

Safety analyses will be descriptive and include rates of ideation according to the Columbia Suicide Severity Rating Scale (CSSR-S) and scores on the Negative Effects Questionnaire. Since this is an open trial, and we do not link these ratings to change in the intervention (e.g. discontinuation) these are for descriptive purposes and for triage in the case of the CSSR-S (see Suicide Safety protocol)

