1.3 SCHEDULE OF ACTIVITIES (SOA)

All activities listed will be administered on both sites.

	Screening Day -7 to -1	Baseline Day 0	Study Visit 2 Day 56 +/- 14 day	Study Visit 3 Day 84 +/- 14 day	Final Study Visit 4 Day 112 +/- 14 day
Procedures					
Informed consent	X				
SCID-5	X				
WRAT-4	X				
Demographics		X			
Medical history		X			
BACS		X			
VRFCAT		X			
MINI		X			
PSQI		X			
WHODAS 2.0		X			
PHQ-9		x			
PANSS		X	X	X	X
Calgary Depression Scale (CDSS)		X	X	X	X
Treatment Rationale Scale		X	X	X	X
CSSR-S		X	X	X	X
IA on METER and VLMT		X	X	X	X
Metacognitive WCST		X	X	X	X
Informant-Rated SLOF		X			X
GPS			X	X	X
Compensatory Cognitive Strategies Scale (Informant)		X			X
CAINS Motivation		X	X	X	X
Defeatist Performance Beliefs		X	X	X	X
Client Satisfaction Questionnaire (CSQ)		X	X	X	X
Negative Effects			X	X	X
Trials and Coaching Sessions Completed			X	X	X
HVLT			X	X	X
Metacog ER-40			X	X	X
Brief Regulation of Motivation Scale			X	X	X
Karolinska Sleepiness Scale			X	X	X
GAD-7			X	X	X

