2.3.1 KNOWN POTENTIAL RISKS

Assessment: Participation in the evaluation and responding to questions on the mobile device requires time and attention. Some participants may become bored or fatigued completing the evaluation. Some participants may also become distressed during the psychiatric evaluation, which requires them to discuss their current symptoms, as well as history of their symptoms.

Intervention: Although the blended computerized interventions to be tested in this study are not expected to produce adverse reactions, participants may become bored or fatigued with the intervention procedures. There is a theoretical possibility that improvements in introspective accuracy may engender increases in depression alongside greater awareness of limitations.

Disclosure or Identification of Suicidal Ideation or Intent Harm Self: During structured interviews concerning suicide (via the Columbia Suicide Severity Scale¹² or CSSR-S) or extemporaneous discussion with rater or other staff, participants may disclose a level of risk of harming themselves or others that would require an evaluation for a higher level of care.

Confidentiality/Loss of Privacy: As with any clinical research study, a risk of disclosure of personal material exists. These risks are present in interview and scale-based measures and technology-based data collection.

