8.2 SAFETY AND OTHER ASSESSMENTS

Baseline Assessment: At the baseline assessment, we will collect demographic and social contextual information (e.g., living situation) and we will gather medication data including sedation/sleepiness side effects via the Karolinska scale³⁴ at all assessment points. All participants will continue to receive their current treatments, as determined by their clinical providers throughout the study. We will also administer the Brief Assessment of Cognition in Schizophrenia-App Version (BACS)³⁵ and Virtual Reality Functional Capacity Assessment Tool³⁶ (VRFCAT) to assess global cognition and functional capacity, respectively, at baseline^{37,38}. In some past mobile interventions (with no coaching) adherence was poorer in patients with lower cognitive ability³⁹, so we will explore neurocognitive ability as a moderator. iTEST is designed to accommodate cognitive impairment by including device/app practice, a simplified guided user interface, and bi-weekly coaching. Finally, we will administer the Treatment Rationale Scale⁴⁰ to evaluate expectancies. Participants will receive 20 dollars for completing the screening portion of the baseline assessment and additional 30 dollars for completing the second part of the visit if eligible for a total of 50 dollars.

Symptom Assessments: Depression and psychotic symptoms will be assessed with the Calgary Depression Scale for Schizophrenia (CDSS)⁴¹ and Positive and Negative Syndrome Scale (PANSS)²⁶.

Table 3. Measures, Constructs, and Indicators		
Construct	Measure	Operational Indicator
Sample Characterization/Exploratory Moderators		
Cognition	BACS (Baseline only)	Total Score
Functional Capacity	VRFCAT (Baseline only)	Total Score
Psychotic Symptoms	PANSS Positive and Negative	Total Score
Depressive Symptoms	Calgary Depression Scale (CDSS)	Total Score
Treatment Expectancies	Treatment Rationale Scale	Total Score
Trained Task-Based IA Target (R61,R33)		
Trained Task-based IA	IA on METER and VLMT	Estimated vs Actual correct
Transfer of Training Target (R61, R33)		
Untrained Task-based IA	Metacognitive WCST	Global resolution score
Primary Outcome (R33; Exploratory in R61)		
Functional Outcome	Informant-Rated SLOF	Total Score
Secondary Outcomes		
Life space Mobility	GPS	Daily distance from home
Exploratory Mechanisms		
Strategy Use; Motivation and Defeatist Beliefs	Compensatory Cognitive Strategies Scale; CAINS Motivation, Defeatist Performance Beliefs	Total scores

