Exploratory Mechanistic Targets Linking Change in IA to Outcome: We will explore whether iTEST increases the use of strategies with the Compensatory Cognitive Strategies Scale (completed by informants and participants)⁴⁵ as well as motivation measured with Clinical Assessment Interview for Negative Symptoms (CAINS) Motivation and Pleasure (MAP) subscale⁴⁶. We will also explore Defeatist Performance Beliefs (DPAS)⁴⁷, which predict effort⁴⁸ and may improve with more accurate self-awareness of abilities.

Informant Ratings: We have attached to this protocol a standard script for recruitment of informants nominated by the participant. The script details the nature of the study and what is asked of the informant. The script is intended to be read over the phone to the participant and if willing, the questionnaires for informants (SLOF; Compensatory Cognitive Strategies Scale) are administered over the phone immediately thereafter (15-20 minutes). Informants then provide an address where a pay card can be sent. Informants are recruited at baseline and at follow up 16 weeks and receive 15 dollars per occasion for a total of 30 dollars.

Intervention Satisfaction: An adapted Client Satisfaction Questionnaire⁴⁹ keyed to both coaching sessions and mobile intervention components

For safety, we will administer the Columbia Suicide Severity Rating Scale⁵⁰. See suicide safety protocol. Since change in IA could theoretically lead to adverse experiences in some individuals (e.g., *greater awareness>depressed mood*), we will administer the Negative Effects Questionnaire (NEQ)⁵¹ at follow-ups. These are descriptive in nature.

We will also measure Clinical Worsening, which we define a criterion of a score of 96 on the PANSS Total Score or a 30% worsening from previous assessment. These criteria are linked to clinical global impression markers and are standard in acceptance. We will use the same approach as the Suicide

Safety Protocol to response to evidence or worsening as below:

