10.1.5 SAFETY OVERSIGHT

Data Safety Monitoring Board (DSMB) Description: The study will have an DSMB. The PIs will monitor and collect information on adverse events (AEs), serious adverse events (SAEs), and/or unanticipated problems. A Data Safety Monitoring Board (DSMB) comprised of independent members will monitor study safety. We will use an established DSMB that monitors clinical studies in our laboratory. The DSMB consists of three members who are external to UCSD, UTD or UM, chaired by a leading expert in clinical trials in serious mental illness, a biostatistician and clinical trials methodologist, and a director of a mental health advocacy organization.

DSMB Provisional Charter: The Board will 1) Meet semi-annually in the first year, and then annually via teleconference (and email correspondence as needed) to first comment on the protocol prior to any enrollment, and finalize the DSMB Charter. Subsequent meetings will then review reports on protocol progress and adverse events; 2) Review developing outcome data. The PIs will provide subject data tables for primary target and outcome variables, including reasons for missing data, forms completion, and review data Quality Control/Quality Assurance procedures at annual meetings. In addition summary responses to the *Negative Experiences Questionnaire*, a measure of side effects in digital health, will be included for both conditions; 3) Review AEs/SAEs according to the convention detailed below; 4) Review participant enrollment progress and dropouts: PI will provide current CONSORT diagram with reasons for dropouts/losses to follow-up and attached dropout table at annual meetings. The DSMB will make recommendations based on review of 1-4 above, regarding appropriate protocol, operational, or other changes, and including reporting deviations or other AEs/SAEs/Unexpected problems related to the study protocol to the appropriate agency/institute (IRB, NIH). The PI will ensure that the IRB is notified of any AEs/SAEs/Unexpected problems, and that the NIH is informed of actions, if any, taken by the DSMB or IRB as a result of its continuing review. The PI will generate minutes of DSMB meetings, including a summary of any discussion of AEs/SAEs or Unexpected problems, and enrollment/dropouts, which will be reviewed and approved by the DSMB Chair, and these minutes will be transmitted to the IRB by the PI or Sub-PI at each site at the time of continuing annual IRB review of the protocol.

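### The CDSS, the only depression scale repeated from baseline, has no planned analysis of change, so the trial can reach 'go' with no estimate of whether depression worsened

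*Combined protocol and SAP*

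**What the plan says.** Section 2.3.1 lists boredom and fatigue as intervention risks and then one risk that follows from the mechanism itself: "There is a theoretical possibility that improvements in introspective accuracy may engender increases in depression alongside greater awareness of limitations". Section 8.2 repeats the idea as the reason for giving the NEQ: "Since change in IA could theoretically lead to adverse experiences in some individuals (e.g., *greater awareness>depressed mood". Section 8.3.3.1 says the same.

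Section 8.2 also states that "Depression and psychotic symptoms will be assessed with the Calgary Depression Scale for Schizophrenia (CDSS") and the PANSS. The Schedule of Activities (Section 1.3) marks the CDSS at baseline and at Days 56, 84 and 112. The PHQ-9 is marked at baseline only, and the NEQ at the three follow-ups only.

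Table 3 in Section 8.2 places the CDSS total under "Sample Characterization/Exploratory Moderators", not under outcomes or side effects. Section 9.4.4 makes the safety analysis descriptive and says that it will "include rates of ideation according to the Columbia Suicide Severity Rating Scale (CSSR-S) and scores on the Negative Effects Questionnaire". Section 10.1.5 describes what the DSMB sees: "The PIs will provide subject data tables for primary target and outcome variables", plus NEQ summaries, AEs and SAEs, enrolment and dropouts. The CDSS is named in neither section. The go/no-go criteria in Section 3 are adherence, IA on the trained tasks and IA on the WCST.

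**The concern.** The trial decides whether to proceed to a randomised R33 trial and at what duration. Success means that IA has risen, which is the condition under which the protocol says mood might fall. The direct way to look for that is change from baseline on a depression scale at the visits where IA is judged. Those data will be collected, but no section commits anyone to analysing them.

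The measures that are analysed answer other questions. An NEQ total with no pre-treatment value gives no change in depression. Ideation rates do not register depressive worsening without ideation. AE reports depend on an event being recognised and recorded. The clinical-worsening definition in Section 8.2 uses the PANSS total. A 'go' could therefore be declared, and a duration chosen, with the named harm never estimated on the scale best placed to show it.

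**Working it through.** **1. Where depression could be picked up**

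| Source | Baseline value? | In 9.4.4? | In DSMB list (10.1.5)? | Gives change in depression? |
|---|---|---|---|---|
| CDSS | Yes, then Days 56, 84, 112 | No | No | Yes |
| PHQ-9 | Yes, baseline only | No | No | No |
| NEQ total | No, follow-ups only | Yes | Yes | No |
| C-SSRS ideation | Yes, all visits | Yes | Not named | No, ideation only |
| AE/SAE reports | Not a scale | Not named | Yes | No |

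The CDSS is scheduled at 4 of 4 assessment visits and has 0 planned analyses of change. Of the 3 go/no-go criteria, 0 concern safety.

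**2. The plan's own figures**

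The documents give no figure for depression or the CDSS. The nearest is in Section 9.2: power for a trained-task IA change of 0.5 SD, from .91 (48 participants, 8 weeks) to .97 (60 participants, 16 weeks). It comes from a three-level simulation whose variance components and alpha are not stated, so it cannot be reproduced. As a rough comparison only, take a paired t-test of d = 0.5, with SD of change equal to the baseline SD and an assumed two-sided alpha of 0.05. It gives 0.924 at n = 48 and 0.968 at n = 60. Those power figures are not in dispute here.

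**3. Precision of mean CDSS change at the planned size**

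Inputs: n = 60, or 48 after 20% attrition (Section 9.2). The baseline-to-follow-up correlation r is not in the documents and is assumed to lie between 0.3 and 0.8. Equal SDs at both times and complete pairs are also assumed.

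- SD of change, in baseline SD units: √(2(1 − r)).
- 95% CI half-width: t(0.975, n − 1) × √(2(1 − r)) / √n.
- Example, r = 0.5: SD of change = 1. For n = 60, 2.001/7.746 = 0.258. For n = 48, 2.012/6.928 = 0.290.

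| r | SD of change | Half-width, n = 60 | Half-width, n = 48 |
|---|---|---|---|
| 0.3 | 1.183 | 0.306 | 0.344 |
| 0.5 | 1.000 | 0.258 | 0.290 |
| 0.7 | 0.775 | 0.200 | 0.225 |
| 0.8 | 0.632 | 0.163 | 0.184 |

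An observed mean worsening of 0.5 SD, the size the trial treats as meaningful for IA, would have an interval excluding zero in every cell. In the least favourable one the lower limit is 0.5 − 0.344 = 0.156 SD.

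**4. Individual worsening**

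A mean near zero can hide a minority who worsen. For illustration, if about 10% worsened by whatever definition the team adopts, the exact 95% CI would be 3.8% to 20.5% (6 of 60) or 3.5% to 22.7% (5 of 48). With no such participant, the upper limit is 6.0% (n = 60) or 7.4% (n = 48).

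**5. Association of CDSS change with IA change**

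Smallest correlation detectable with 80% power, two-sided 0.05 (assumed), by Fisher's z: tanh((1.960 + 0.842)/√(n − 3)). For n = 60, tanh(2.802/7.550) = 0.355. For n = 48, tanh(2.802/6.708) = 0.395. Only correlations of about 0.36 to 0.40 or more are within reach.

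**The case against.** A reader might infer that the named harm is left out of the safety analysis and of DSMB review altogether. The documents do not support that. Sections 8.2 and 8.3.3.1 give the NEQ expressly because of depressed mood following greater awareness, and the NEQ is in both Section 9.4.4 and Section 10.1.5. What is missing is an estimate of change in depression.

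Nor would depressive worsening be invisible. Section 8.3.4 has the investigator ask about AEs at each visit, Section 7.1 treats new clinically relevant findings as AEs, and the DSMB reviews AEs and SAEs. These routes are real, but none yields a change on a depression scale.

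Three further points limit how much weight the omissions carry. The wording of Section 9.4.4 is not strictly exhaustive. Section 9.4.9 marks exploratory analyses as not applicable, but it also omits exploratory work promised in Section 8.2, so its silence proves little. The DSMB list belongs to a provisional charter. All this stands, yet no other section plans the CDSS analysis, and Section 9.4.1 says there is no formal SAP that might supply it.

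Finally, this is a single-arm pilot, the harm is called theoretical, and the go/no-go criteria concern adherence and target engagement by design. CDSS change could not be attributed to iTEST. That limits interpretation, but the same limit applies to the IA changes on which the decision rests, and it is no reason to leave the estimate out.

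**Conclusion.** The point holds as a specific gap in the safety analysis. The only depression scale repeated from baseline has no planned analysis of change, and the harm named in Section 2.3.1 is covered only by NEQ totals without a baseline, C-SSRS ideation rates and AE reports. The R61 can reach 'go' without anyone having estimated whether depression worsened.

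The gap is not forced by sample size: mean change would be known to within about 0.16 to 0.31 baseline SD at n = 60 and 0.18 to 0.34 at n = 48. These figures rest on the assumed correlation of 0.3 to 0.8, equal SDs and complete pairs. The textual finding rests on no assumption. The gap does not affect the primary endpoints, and it does not show that iTEST worsens mood. It should be closed because the better data will already be in hand.

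**What to change.** - In Section 9.4.4, add descriptive CDSS change from baseline at weeks 8, 12 and 16: the mean with 95% CI, the number contributing at each visit, and the distribution of individual changes. The distribution matters because Section 8.2 speaks of harm in some individuals, which a mean can miss.
- Add the same summaries to the DSMB tables in Section 10.1.5 when the charter is finalised.
- Optionally, report the association of CDSS change with IA change as exploratory. State that a single arm cannot attribute change to iTEST and that only correlations of about 0.36 to 0.40 or more are detectable with 80% power.
- Optionally, show CDSS change beside the go/no-go result. This adds no criterion.

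No clinical rule or threshold is proposed. The cost is a few lines of text and a small amount of extra analysis, with no new visits, instruments or staff.

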9.4.5 BASELINE DESCRIPTIVE STATISTICS

Not applicable as this is an open single arm trial.

9.4.6 PLANNED INTERIM ANALYSES

Not Applicable

9.4.7 SUB-GROUP ANALYSES

There are no plans to evaluate endpoints by age, sex, race/ethnicity, or other demographic characteristic(s). This is a pilot study and therefore the study is underpowered to detect an effect variation by subgroup.

9.4.8 TABULATION OF INDIVIDUAL PARTICIPANT DATA

Individual participant data will not be listed by measure and time point.

9.4.9 EXPLORATORY ANALYSES

Not Applicable

10 SUPPORTING DOCUMENTATION AND OPERATIONAL CONSIDERATIONS

10.1 REGULATORY, ETHICAL, AND STUDY OVERSIGHT CONSIDERATIONS

Leave blank. Text should be included under the relevant subheadings below.

10.1.1 STUDY DISCONTINUATION AND CLOSURE

The only foreseeable reasons for termination/suspension would be if an unexpected significant risk was revealed. As this is a pilot study other criteria (futility, etc.) are not relevant.

Circumstances that may warrant termination or suspension include, but are not limited to:

- Determination of unexpected, significant, or unacceptable risk to participants

Study may resume once concerns about safety, protocol compliance, and data quality are addressed, and satisfy the sponsor, IRB and/or Food and Drug Administration (FDA).

10.1.2 CONFIDENTIALITY AND PRIVACY

Participant confidentiality and privacy is strictly held in trust by the participating investigators, their staff, and the sponsor(s) and their interventions. This confidentiality is extended to cover testing of biological samples and genetic tests in addition to the clinical information relating to participants. Therefore, the study protocol, documentation, data, and all other information generated will be held in

strict confidence. No information concerning the study or the data will be released to any unauthorized third party without prior written approval of the sponsor.

All research activities will be conducted in as private a setting as possible.

The NIH and the Institutional Review Board (IRB), may inspect all documents and records required to be maintained by the investigator, including but not limited to, medical records (office, clinic, or hospital) for the participants in this study. The clinical study site will permit access to such records.

The study participant's contact information will be securely stored at each clinical site for internal use during the study. At the end of the study, all records will continue to be kept in a secure location for as long a period as dictated by the reviewing IRB, Institutional policies, or sponsor requirements.

Study participant research data, which is for purposes of statistical analysis and scientific reporting, will be transmitted to and stored at the National Data Archive. This will not include the participant's contact or identifying information. Rather, individual participants and their research data will be identified by a unique study identification number called a GUID. The study data entry and study management systems used by clinical sites and staff will be secured and password protected. At the end of the study, all study databases will be de-identified and archived at the National Data Archive.

Certificate of Confidentiality

To further protect the privacy of study participants, a Certificate of Confidentiality will be issued by the National Institutes of Health (NIH). This certificate protects identifiable research information from forced disclosure. It allows the investigator and others who have access to research records to refuse to disclose identifying information on research participation in any civil, criminal, administrative, legislative, or other proceeding, whether at the federal, state, or local level. By protecting researchers and institutions from being compelled to disclose information that would identify research participants, Certificates of Confidentiality help achieve the research objectives and promote participation in studies by helping assure confidentiality and privacy to participants.

Confidentiality for In-Lab Assessments: In order to protect confidentiality all participant data will be de-identified by providing each participant a unique ID in computer files and all physical files from the study will be kept in a locked cabinet in our research offices. All electronic data and files will be stored on a secure server also housed at UCSD. Only study investigators and trained research personnel linked to this study and registered with the IRB will have access to this data. All documentation will identify participants by their Unique ID number and not other personally identifying information.

Confidentiality and Privacy Protections for Mobile Device Data: Mobile health interactions are transmitted in an encrypted fashion and devices used in this research will not contain or transmit personally identifying information with study data. Since the study platform uses a web-based data collection engine, there is no data that is stored on the device. We will use HIPAA compliant Amazon Web Services (AWS) to schedule the iTEST skills training, surveys and for data usage. AWS offers a simple and intuitive web-based user interface from user to server. It is an easy-to-use cloud-computing platform that allows various storage services for backup, archiving, and disaster recovery use cases. AWS enables robust safeguards to help protect the privacy of the data with highly secure AWS Data centers.

Amazon S3 provides scalable and durable object storage in the cloud. S3 is where the experimenters will be storing the user information (study ID number, phone number, start and end time) along with the survey links. Once the data is generated, the data will be stored securely in this server, which will only be accessible by study staff. Study staff will utilize queries in Amazon's Athena to extract key variables of interest in the mobile cognitive tests. We will also be using Postman to send the surveys to our users in the form of text messages. Postman is a popular API client that makes creating, sharing, and documenting APIs simpler. This is done by creating and saving HTTPs requests via python. A group of saved requests can be organized into folders or "collections". From this collection, experimenters are able to adjust the code to send the survey links to certain participants at a specific start date and end date to their mobile numbers. By saving these API requests, we will not have to remember the endpoint of the API, API key, etc. – as such the information is not connected to PII. All PIs and study staff will have access to these platforms and will ensure that the data is secure.

Finally, it is possible that some participants may store data (e.g., notes) on the device provided to them if they opt not to use their own device or do not have one. Individuals are informed of this risk, and should the participants lose the study device, we have taken the additional step of incorporating the Autowipe application on all study devices which enables remote factory reset of the device, erasing all data. An additional safeguard for privacy loss is the use of a homescreen "lock" such that participants must enter a brief code to operate the equipment. If participants lose or damage study device, they will not be held responsible for the cost of the device or any other costs.

